#### 11.1.5 Secondary Efficacy Analyses

All secondary variables assessing a mean absolute or a mean relative change will follow a similar methodology as for the primary variable; i.e., mean changes of ESS (up to 2-week treatment period), SCOPA-Sleep (up to 2-week and 6-week treatment period), PDSS-2 (2-week and 6-week), MWT (6-week), polysomnography (6-week), UPDRS Part III (2-week and 6-week), motor function assessed by the wrist worn device (6-week), HAM-D (2-week, 6-week and follow-up), MoCA (6-week), and FSS (6-week).

The percentage of subjects who showed ESS clinical response (defined as an ESS decrease from baseline of at least 3.0 points and/or final ESS score ≤10) after 2 and 6 weeks of treatment will be described and compared between groups by means of a Chi-square test (or Fisher's exact test according to corresponding applicability). Percentages and difference between treatments will be expressed with their 95% confidence interval calculated with a binomial exact method.

# 11.1.6 Exploratory Analyses

All variables obtained with the wearable tool assessing a mean absolute or a mean relative change will follow a similar methodology as for the primary variable. Categorical variables will be described and compared between groups by means of a Chi-square test (or Fisher's exact test

Amendment 04, Final Version 1.0 07/Nov/2018 Page 81 / 142

according to corresponding applicability). Percentages and difference between treatments will be expressed with their 95% confidence interval calculated with a binomial exact method.

Both univariate and multivariate statistical methods will be used as an exploratory pharmacogenomic analysis in order to identify genetic reasons why certain people respond differently to Bavisant, to find out more information about how Bavisant works, and to generate information needed for research, development, and regulatory approval of tests to predict response to Bavisant, and to identify variations in genes related to the biological target of Bavisant.

### 11.1.7 Safety Analyses

Adverse events, adverse events of special interest, serious adverse events, serious and related adverse events will be coded using the latest available MedDRA version and their corresponding incidences will be summarised as overall events, related events, and events by intensity. AEs will be summarised by MedDRA preferred term and system organ class (primary SOC). Summaries of AEs by preferred term and decreasing frequency and by maximum severity will also be prepared.

Physical examination changes, vital signs changes, laboratory tests changes, cardiovascular changes, ocular changes, suicidal ideation (C-SSRS) findings, and positive psychotic symptoms (BPRS+) findings will be described for the different treatment groups and assessed as either clinically or non-clinically significant findings.

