# 8.4.1.6 Physical examination

Complete physical examination will be performed at screening and visit 3 (day 42) or early termination. Physical examinations will consist of the following body systems: (1) general appearance; (2) extremities; (3) skin; (4) head and neck; (5) eyes, ears, nose and throat; (6) lungs and chest; (7) heart/ cardiovascular; (8) neurological; (9) abdomen / gastrointestinal; (10) liver; (11) musculoskeletal; and (12) other. Each system should be assessed as normal or abnormal and in this last case if that is clinically relevant or not.

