The BPRS consists of 4 symptom constructs ((#4, #11, #12, and #15) which ranges from 1 (not present) to 7 (extremely severe). 0 is entered if the item is not assessed. The total score is calculated as the sum of the scores of the 4 items. Incidence of patients with an increase and incidence of patients with a decrease from baseline in the BPRS+ total score will be described at the corresponding visit. Also the change from baseline will be descriptively analysed as a numerical data (see section 7 for further reference) for all patients, for patients with BPRS+ total score reduction and for patients with BPRS+ total score increase.

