12.4 Incidence of physical examination, vital signs

Physical examinations will consist of the following body systems: (1) general, appearance; (2) extremities; (3) skin; (4) head and neck; (5) eyes, ears, nose and throat; (6) lungs and chest; (7) heart/ cardiovascular; (8) neurological; (9) abdomen / gastrointestinal; (10) liver; (11) musculoskeletal; and (12) other. Each system should be assessed as normal or abnormal and in the last case if that is clinically relevant or not. The incidence of patients with at least one change from normal at baseline to abnormal at Visit 3 will be calculated for each of the body systems.

Potentially Clinically Significant Abnormality (PCSA) are detailed below for Vital signs:

- WEIGHT change from baseline >5%
- Number of breaths per minute <12 or >25. Percentages of patients with a normal respiratory rate (RR) at baseline and an abnormally high or low RR at Visit 3 will be summarized by treatment.

Incidences will be calculated using the number of patients in the safety population as denominator.

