12.7 Incidence of eye exam findings

Incidence of patients with any new finding on ophthalmological examination in the follow up period will be calculated. Detailed listings of all baseline and on-treatment ophthalmological findings will be provided

Incidences will be calculated using the number of patients in the safety population as denominator.

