14 CHANGES FROM THE PROTOCOL

There are no changes to the statistical content specified in the protocol.

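### SAP summaries for physical examination, laboratory, eye, C-SSRS and BPRS+ findings omit the clinical-significance class that Protocol 11.1.7 requires, and SAP 14 does not declare it

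*Protocol*

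**What the plan says.** Protocol 11.1.7 names seven kinds of safety result (physical examination, vital signs, laboratory, cardiovascular, ocular, C-SSRS and BPRS+) and says that they "will be described for the different treatment groups and assessed as either clinically or non-clinically significant findings". The synopsis has the same sentence.

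For the physical examination, Protocol 8.4.1.6 requires the rating on which such a class would rest: "Each system should be assessed as normal or abnormal and in this last case if that is clinically relevant or not". SAP 12.4 repeats that instruction and then defines an output that does not use it: "The incidence of patients with at least one change from normal at baseline to abnormal at Visit 3 will be calculated", separately for each body system.

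For BPRS+, SAP 12.3 reports "Incidence of patients with an increase and incidence of patients with a decrease from baseline in the BPRS+ total score" and adds a numerical summary of the change for all patients, for those who fell and for those who rose. For the eye, SAP 12.7 says: "Incidence of patients with any new finding on ophthalmological examination in the follow up period will be calculated", and promises full listings. SAP 12.5 gives laboratory shift tables against the normal range. SAP 12.2 counts subjects with any positive C-SSRS answer.

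SAP 12.4 (weight, respiratory rate) and 12.6 (blood pressure, heart rate, QT, QTc) do set limits for potentially clinically significant abnormalities (PCSA). SAP 14 states: "There are no changes to the statistical content specified in the protocol".

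**The concern.** The protocol promises a separation between findings that matter clinically and findings that do not. In five of the seven domains the SAP asks for no such separation. In one of those five it restates the rating and then leaves it unused.

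Protocol 6.2.2 defines the safety endpoints as incidences of findings. BPRS+ was added in Amendment 03 in answer to the FDA's safety review, and the eye examination was kept in Amendment 02 when the lens grading was removed. If the incidence is a count of any change, a few important events in one dose arm sit inside a background of minor changes that all arms share. A reader comparing the study report with the protocol would also find the promised class absent, with no departure declared.

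**Working it through.** There is no sample size, power or alpha figure to reproduce. The check is a comparison of texts, plus the arithmetic of the BPRS+ scale.

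**Step 1. Domain by domain.**

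| Domain | Rating in the protocol | SAP summary | Significance criterion in SAP |
|---|---|---|---|
| Physical examination | Relevance rated (8.4.1.6) | Normal-to-abnormal change (12.4) | No |
| Vital signs | Not specified | PCSA limits (12.4) | Yes |
| Laboratory | Relevance rated; relevant values become adverse events (8.4.1.10) | Shift against normal range (12.5) | No |
| Cardiovascular | ECG findings go to medical history or adverse events (8.4.1.12) | PCSA limits (12.6) | Yes |
| Eye | Abnormalities noted, no rating specified (8.4.1.13) | Any new finding, plus listings (12.7) | No |
| C-SSRS | No rating specified | Any positive answer (12.2) | No |
| BPRS+ | No rating specified | Any rise, any fall, plus numerical change (12.3) | No |

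Two of seven domains have a criterion and five do not.

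**Step 2. Could a version difference explain it?** SAP 1 refers to Amendment 03. The amendment log shows that the synopsis sentence, with C-SSRS and BPRS+ included, was in force at Amendment 03. So the requirement was in the version on which the SAP is based.

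**Step 3. Physical examination.** Each body system has three possible states: normal, abnormal but not relevant, abnormal and relevant. That gives three ways to worsen:

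- normal to abnormal, not relevant: counted
- normal to abnormal, relevant: counted, and not distinguishable from the line above
- abnormal, not relevant, to abnormal, relevant: not counted

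Of the two routes that end in a relevant finding, one is merged with trivial changes and the other is lost. The loss may matter most for the neurological system. Protocol 18.2 requires bradykinesia plus a further motor sign for the diagnosis, so many subjects may be abnormal there at baseline. That is an inference; the documents give no baseline rates.

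**Step 4. BPRS+.** Four items scored 1 to 7 give a fully assessed total from 4 × 1 = 4 to 4 × 7 = 28, a span of 24. The rise count therefore gives the same weight to 1 point (1/24 = 4.2% of the span) and to 24 points.

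SAP 12.3 also records an item that was not assessed as 0 and defines the total as the sum of the four items, without excluding zeros:

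- Baseline 0 + 1 + 1 + 1 = 3, later 1 + 1 + 1 + 1 = 4. Change +1, counted as an increase with no symptom present.
- Baseline 1 + 1 + 1 + 1 = 4, later 0 + 2 + 1 + 1 = 4. Change 0, although one item rose.

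**Step 5. How far a count can be blurred (illustration only).** Assume important changes in 2% of one arm and 12% of another, with an independent background b of trivial changes equal in both. The observed proportion is 1 − (1 − p)(1 − b).

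| b (assumed) | p = 2% | p = 12% | Ratio |
|---|---|---|---|
| 0% | 2.0% | 12.0% | 6.0 |
| 10% | 11.8% | 20.8% | 1.76 |
| 20% | 21.6% | 29.6% | 1.37 |
| 40% | 41.2% | 47.2% | 1.15 |

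None of these rates comes from the documents. The table fits a domain with a single count, such as BPRS+ or eye. The physical examination is counted by body system, so its background per row would be lower.

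**The case against.** A reader might infer that the SAP drops clinical significance from safety reporting altogether, or that no safety conclusion can be drawn from its tables. The documents do not support either reading.

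- Vital signs and cardiovascular findings have PCSA limits. These are numerical limits and not investigator ratings, but they serve the same purpose.
- The size of BPRS+ change is summarised, including among those who rise, with mean, quartiles and maximum (SAP 12.3 and 7). A large rise would be visible there.
- Eye findings are listed in full.
- The general adverse-event rules (Protocol 9.1.1, 9.1.2, 9.7) are broad enough to take in an important psychotic symptom, eye disease or examination abnormality, and adverse events are summarised by intensity. Relevant laboratory values become adverse events by explicit rule.
- SAP 12 makes safety descriptive, with no systematic testing, so no test is weakened.
- The protocol gives no criterion for a clinically significant BPRS+, C-SSRS or eye finding. In those domains the gap begins in the protocol.
- Table shells are a separate document (SAP 17) and could contain the class. The protocol sentence can also be read as asking for an assessment without demanding a table of it by arm.

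All of this limits the consequence. It does not remove the mismatch. The adverse-event route depends on an investigator choosing to report; no specific rule sends physical examination, eye or BPRS+ findings there, and Protocol 8.4.1.13 records eye abnormalities in the clinical notes. The SAP text does not ask the shells for a class. On the looser reading of the protocol, SAP 12.4 still restates a rating and specifies no output that uses it.

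**Conclusion.** The point holds in limited form. Five of seven domains lack the class that Protocol 11.1.7 states, and SAP 14 is wrong to declare no change. The physical examination is the firmest part: a required rating is unused, trivial and relevant changes are merged, and one kind of relevant worsening is missed. The BPRS+ scoring of 0 is a separate small defect that follows from the SAP as written.

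The effect on the trial's safety reading cannot be sized from the documents. The dilution figures rest entirely on assumed rates and describe a blurred descriptive count, not a failed test. The conclusion also assumes that the unseen table shells add nothing beyond the SAP text. The gap is worth closing before unblinding, but it does not make the safety tables uninterpretable.

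**What to change.** - **SAP 12.4 and 12.5:** beside the existing summaries, add by arm the number and percentage of subjects with a new or worsened finding rated clinically relevant. For the physical examination, count a system rated relevant at Visit 3 that was normal, or abnormal but not relevant, at baseline.
- **SAP 12.3:** add by arm the distribution of the highest post-baseline rating (1 to 7) on any of the four BPRS+ items. Treat 0 as missing, not as a score, and state how a total with a missing item is handled.
- **Eye, C-SSRS and BPRS+:** the protocol specifies no rating, so either fix a classification before unblinding or declare that none will be applied. The blinded data review in SAP 6 is a convenient point for this.
- **SAP 14:** replace the statement of no change with the actual departures.

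SAP 12.6 needs no change. The cost is SAP wording and extra table rows. Physical examination and laboratory need no new data, because the protocol already requires those ratings. A classification of eye, C-SSRS or BPRS+ findings would need a short written rule and some blinded review time.

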#### 11.1.8 Other Analyses

No other analyses are planned.

#### 11.2. Determination of sample size

A total of 200 completed subjects will be evaluated for the study (50 completed subjects per treatment group, with expected early withdrawal rate of around 15%).

The assumptions used for the sample size calculation are a mean absolute change in the Epworth Sleepiness Scale (ESS) from baseline to the end of the 6-week treatment period of at least 3.0 points (minimum change considered as clinically relevant) and a standard deviation of 5.0 (based on a comparable study of Modafinil in a similar population recruited at one centre which showed a standard deviation in the ESS between 3.5 at baseline and 4.8 at the end of the treatment period) and a reduction in ESS of 2.7 points for subjects treated with Modafinil.

The confirmation of the hypothesis of detecting a mean difference in ESS of 3.0 points vs. baseline requires a sample size of 25 subjects per group (intragroup  $\Delta$ =3.0; SD=5.0; two-side  $\alpha$ =0.05;  $\beta$ =0.20; power=80%; one-sample t-test).

The additional endpoint of showing a statistically significant difference of at least 3.0 points in ESS between Bavisant and. placebo requires a sample size of 50 subjects per group (between treatment  $\Delta$ =3.0; SD=5.0; two-side  $\alpha$ =0.05;  $\beta$ =0.20; power=80%; two-sample equal-variance t-test).

Amendment 04, Final Version 1.0 07/Nov/2018 Page 82 / 142

The effect size of Bavisant in EDS is unknown and smaller changes in ESS may be clinically useful according to its profile, and higher variability is expected in this multicentre study; so the sample size of 200 completed subjects (50 per treatment group) is proposed in order to cover both the confirmation of an intragroup change of at least 3.0 points vs. baseline, and the between-group difference of at least 3.0 points change vs. placebo.

The Maintenance of Wakefulness Test (MWT) will be performed in a minimum of 20 subjects per group (80 overall) in order to be enough to show statistically significant differences if the expected MWT absolute change from baseline differs at least in one standard deviation (effect size = 1.0).

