### 7.0 Investigational Plan

# 7.1. Overall Study Design and Plan: Description

This phase 2b study is designed as multicentre, multinational, randomized, double blind, parallel group and placebo controlled with three doses of Bavisant (0.5, 1, and 3 mg/d) in subjects with excessive daytime sleepiness with Parkinson's disease. This study will involve approximately 230 subjects from around 48 sites globally.

Eligible subjects will be randomly allocated at a ratio of 1:1:1:1 to either Bavisant (at doses of 0.5, 1, and 3 mg/d) or placebo.

After signing the study informed consent, subjects meeting the UK PDS Brain Banks Diagnostic Criteria for Parkinson's disease (see details in Appendix 18.2) will enter a screening period (lasting up to 3 weeks) followed by a baseline period (lasting up to 1 week). Key inclusion / exclusion criteria will be verified to determine subject eligibility at the screening, baseline periods and prior to randomisation, including the suicide risk assessment following the FDA Guidance for Industry on Suicidal Ideation and Behavior.

[figure not shown]
There is a 6 weeks treatment period, starting on Day 1, followed by a safety follow-up at least 4 weeks after completion of the treatment period. Additional unscheduled visits may be required based on the investigators' judgement at the end of study visit or at the safety follow-up. For early termination, all the assessments of the treatment week 6 visit should be performed, if possible, including the safety follow-up 4 weeks after the last IMP administration.

A schematic of the study design is included in Figure 1 and the schedule of assessments is listed in Appendix 18.15.

Protocol No.: BB-2001-201b 07/Nov/2018 EudraCT No.: 2017-000877-35 Page 39 / 142

Figure 1. Study figure

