The effect size of Bavisant in EDS is unknown. Smaller changes in ESS may be detected that may be clinically useful. In addition, although higher variability is expected in this multicentre study, variability may be lower as the selection criteria restricts a baseline ESS > 12.0 points (compared to 10.0 by other studies). Therefore, in order to confirm both the intragroup statistical decrease in daytime sleepiness together with the intergroup statistical comparison vs. placebo, a total sample size of 200 completed subjects (50 per treatment group + expected 15% of early withdrawal rate) is proposed in this planned first study. The study will be powered to detect a minimum 3.0 point difference in the ESS change from baseline compared to placebo assuming an SD range from 4.0 to 5.3 ( $\alpha$ =0.05;  $\beta$ =0.20; power=80%;  $\Delta$ =3.0; SD=5.0).

Finally, a placebo control group has been considered relevant for the study among other reasons because the primary endpoint is a self-reported assessment, subjective by nature. This subjectivity is controlled by intra-subject comparisons compared to baseline score, and by statistical methods (ANCOVA and MMRM models); but an additional control group with placebo could be considered as the natural progression of the EDS within a clinical trial environment. In any case, the subjects will be informed about the possibility of receiving placebo, the possible consequences and their right to withdraw from the study at any time.

Amendment 04, Final Version 1.0
Protocol No.: BB-2001-201b
EudraCT No.: 2017-000877-35
Page 43 / 142

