#### 11.0 Statistical Methods and Determination of Sample Size

#### 11.1. Statistical and analytical plans

The statistical analysis will be performed by the Department of Biostatistics of Linical, using SAS® version 9.2 or later.

Statistical significance will be assessed for two-sided probability values < 0.05.

All descriptive variables will be tabulated. Quantitative variables will be described showing their number of available and missing observations, mean, median, standard deviation (SD), the range (minimum and maximum) and the first and third quartiles. Frequency and percentage will describe qualitative variables. Missing values will be tabulated with their frequency but will not be included in the calculation of percentages.

The main population for the efficacy analysis will be the intent to treat population (ITT). The per protocol population (PP) will be analysed also as a sensitivity analysis.

The main population for the safety analysis will be the safety population (SAF), defined as all the subjects who have received at least one dose of study treatment.

Full details of the statistical analysis will be given in a Statistical Analysis Plan (SAP) which will be prepared, approved and signed before the database closure, and so before the subjects' evaluability assessment.

Any deviation from the original SAP will be included and reported in the clinical study report (CSR).

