#### 11.1.3 Efficacy Analyses

# 11.1.4 Primary Efficacy Analyses

ESS mean absolute change from baseline to the end of the 6-week treatment period will be analysed with an ANCOVA model, with the baseline ESS as a covariate, region and treatment as a factor. Missing data in the 6-week ESS evaluation will be considered as a treatment failure, that is imputing the missing ESS reduction as 0. Least-squared (LS) absolute mean changes will be presented by treatment group together with their corresponding 95% confidence interval. Paired-comparisons will be performed without any multiplicity adjustment.

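### The sample-size statement says 50 per group are required at SD 5.0 and 80% power; those inputs require 45, and 50 gives 84%

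*Protocol*

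**What the plan says.** Protocol 11.2 gives the between-group requirement as a calculation with every input shown. The aim is "showing a statistically significant difference of at least 3.0 points in ESS between Bavisant and. placebo", which, it says, "requires a sample size of 50 subjects per group". The bracket lists a difference of 3.0, SD 5.0, two-sided alpha 0.05 and "power=80%; two-sample equal-variance t-test". The SD is introduced earlier in that section as "a standard deviation of 5.0 (based on a comparable study of Modafinil in a similar population recruited at one centre". SAP 5 repeats the statement with the same inputs.

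The sample-size paragraph of the synopsis (Protocol 2.0) attaches the same inputs to 50 completed subjects per group, but says this number will be sufficient, not that it is required.

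Protocol 7.2 says the study is powered for a 3.0-point difference "assuming an SD range from 4.0 to 5.3". The bracket closing that sentence again reads SD 5.0 and power 80%.

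After the disputed sentence, 11.2 and SAP 5 add that the effect size is unknown and that variability is expected to be higher in a multicentre study. They propose 200 completers (50 per group) on that basis.

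**The concern.** A sample-size sentence that lists all its inputs should reproduce when they are put back in. This one does not, and the gap is larger than rounding. It is the justification for the primary comparison, and the same inputs appear in 11.2, the synopsis and SAP 5.

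What is at stake is whether 50 per group carries a margin. If 50 were the bare requirement at SD 5.0, there would be nothing in hand against the higher variability the sponsor expects. In fact there is a margin, but the sentence hides it by calling 50 the requirement at 80%.

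**Working it through.** **Inputs**
- Difference 3.0, SD 5.0, 80% power, two-sample equal-variance t-test: Protocol 11.2 and SAP 5.
- Alpha 0.05, two-sided: the same bracket, and Protocol 11.1 ("Statistical significance will be assessed for two-sided probability values < 0.05").
- Equal allocation, so 1:1 for each dose against placebo: Protocol 7.1 ("randomly allocated at a ratio of 1:1:1:1 to either Bavisant").
- Alpha not divided among the three doses: Protocol 11.1.4 ("Paired-comparisons will be performed without any multiplicity adjustment").
- The 50 are completed subjects, so no dropout inflation enters.

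**Method.** With n per group, the degrees of freedom are 2n − 2 and the noncentrality is (3.0/SD) × √(n/2). Power is the probability that a noncentral t variable with these parameters falls beyond the two-sided 5% critical value.

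**Attempt to reproduce 50 at SD 5.0**

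| n per group | SD | df | Noncentrality | Critical t | Power |
|---|---|---|---|---|---|
| 44 | 5.0 | 86 | 2.814 | 1.988 | 79.5% |
| 45 | 5.0 | 88 | 2.846 | 1.987 | 80.4% |
| 50 | 5.0 | 98 | 3.000 | 1.984 | 84.4% |

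The smallest n reaching 80% is 45. The normal approximation gives 2 × (1.960 + 0.842)² × 5.0²/3.0² = 43.6, so 44. Neither gives 50. The gap is 50 − 45 = 5 per group (5/45 = 11%), or 84.4 − 80.0 = 4.4 points of power.

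**Other routes to 50 at SD 5.0**

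| Variant | n per group |
|---|---|
| One-sided alpha 0.05 | 36 |
| 85% power | 51 |
| 90% power | 60 |
| Bonferroni, 2 comparisons | 55 |
| Bonferroni, 3 comparisons | 60 |
| Rank test, relative efficiency 0.955 | 48 |
| Rank test, relative efficiency 0.864 | 53 |
| 45 inflated for 15% dropout, 45/0.85 | 53 |

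None gives 50, and none is the stated method.

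**The SD range in 7.2**

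| n per group | SD | Power |
|---|---|---|
| 50 | 4.0 | 96.0% |
| 50 | 5.0 | 84.4% |
| 49 | 5.3 | 79.2% |
| 50 | 5.3 | 80.0% |

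Fifty is the exact 80% answer at SD 5.3, and 5.30 is the largest SD at which 50 per group keeps 80%. So 50 covers the whole range in 7.2 at 80% or better, while the bracket in that sentence gives the power as 80% at SD 5.0.

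**Companion one-sample figure.** The same section gives 25 subjects for a within-group change of 3.0 at SD 5.0 and 80% power. With noncentrality (3.0/5.0) × √n, 24 subjects give 80.4% and 25 give 82.1%. That agrees to within one subject. At SD 5.3, 25 give only 77.5%, so reading 5.3 for 5.0 throughout would repair the 50 but leave the 25 short.

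**The case against.** The strongest reply is that the documents already explain the 50. The range in 7.2 reproduces it exactly at its upper end. The paragraph after the disputed sentence names higher variability as a reason for proposing 200 completers. Read as a target, 80% is met by 50 at SD 5.0. The one-sample figure is also just above its minimum, so simple rounding up is possible too.

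Much of this stands. A reader might infer that 50 has no basis, or that the design SD is unknown. The documents do not support either. They consistently name 5.0 as the assumed SD, and 5.3 appears once, as the end of a range. A reader might also infer that the reserve for withdrawal is now in doubt. It is not: the 50 are completers, and early withdrawal of about 15% is handled separately by randomising about 230.

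What the reply does not rescue is the sentence itself. It says the bracketed inputs require 50, and they require 45. If 50 includes a margin for variability, it is not the requirement at SD 5.0. Neither 11.2 nor SAP 5 refers to the range that would explain it. The synopsis is less exposed, since 50 is indeed sufficient; only its power label is loose.

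**Conclusion.** The between-group figure in Protocol 11.2 and SAP 5 is wrong for its stated inputs: 45 per group are required, not 50, and 50 completers give 84.4% power, not 80%. In 7.2 the range fits 50 but the bracket does not.

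This is a minor reporting error on the conservative side. It must not be read as a finding that the trial is underpowered or the wrong size, because on the stated assumptions 50 per group exceeds the target. The result assumes the test exactly as stated: equal groups of completers, common SD, two-sided alpha 0.05, no multiplicity adjustment. That SD 5.3 is the source of the 50 is the best fit to the documents, but they do not say so.

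**What to change.** In Protocol 11.2 and SAP 5, replace the sentence with: *45 per group are needed for 80% power at SD 5.0; 50 completed subjects per group were chosen, giving 84% power at SD 5.0 and 80% up to SD 5.3 (difference 3.0, two-sided alpha 0.05).*

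In the synopsis and the 7.2 bracket, align the labels so that SD 5.0 goes with 84% power, or SD 5.3 with 80%.

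The cost is one sentence in each document and two label edits. Enrolment, randomisation and analysis do not change.
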